1. METHODOLOGICAL

Based on the three rules of clinical decision (2 derivatives and one based on the literature review), a prospective observational study will be carried out in the emergency departments of Chicoutimi, Jonquière and Alma. Data collection for this theoretical validation phase has been underway since December 2019, having received the approval of the various local research committees (ethics, scientific and convenience).

Inclusion and exclusion criteria

The inclusion criteria will be: all patients of minor or adult age who have had anaphylaxis that meet the known diagnostic criteria. In addition, if a patient presents with confirmed exposure to an allergen and symptoms that do not yet meet the anaphylaxis criteria, they may be included in the study. This will only be possible if the doctor deems that he will inevitably progress to anaphylaxis and treat him in this way. Those who have had a reaction to taking a drug (e.g. IECA), who are known for a hereditary pathology (hereditary angioedema), immune OR other pathology giving an anaphylactoid reaction will be excluded, as in Phase 1 of the study.

Sample size

The required sample size was adjusted for the primary objective based primarily on the study of sensitivity and specificity. As a low prevalence of biphasic reactions is expected, a calculation based on specificity is useless, therefore to be rejected. Thus, using the statistician involved in the study and using a sample size calculation adapted for a confidence interval on a ratio adjusted according to the Buderer¹³ formula, it was determined that it was necessary to have 553 patients in total to estimate a sensitivity of at least 98% with a confidence level of 95% according to an accuracy of 5% and an expected prevalence of 6%. Note that a 10% rate was added to the initial size calculation to manage the possibility of missing data. The prevalence of 6% was determined from the prevalence of biphasic reactions observed when collecting Phase 1 data from the same study..

Data collection

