In the face of a case of anaphylaxis, the doctor will have to answer a short questionnaire developed with the variables present in each of the three rules (questionnaire available in appendix). The variables were randomly arranged on the questionnaire so that no rules could be recognized or inferred. If the doctor deems that a patient who does not yet present the anaphylaxis criteria, but in the absence of ahead, will eventually progress to real anaphylaxis, he or she will have to indicate it at the appropriate location on the questionnaire. Indeed, as mentioned above, these patients will be included in the study, but we will independently analyze the results of this sample to determine if they are different from the overall results in subgroup analyses.

The questionnaire will be available at several key locations, including in the paper-based resuscitation rooms in the three emergencies where data collection will take place. The questionnaire will also be systematically placed on the file of patients with suspected anaphylaxis at triage. The doctor will be required to complete the questionnaire anonymously, but will be required to provide the patient's file number. This will be done after the initial stabilization. After completing the questionnaire, the physician will simply be able to continue to care for the patient as he would have done in accord with his standard clinical practice. No decision rules will be applied to patients. The answers provided to

the questionnaire will therefore have no impact on the clinical decisions made by the treating physician. The research team will then review each of these files to assess whether or not there was a biphasic reaction and whether it was clinically significant (according to the NIAID/FAAN²criteria).

At the next emergency department meetings involved, doctors will be notified of the operation of the current study. Recalls will be made as required during the course of the study to ensure the involvement of the medical profession. Administrative officers and triage nurses will also be advised to add the questionnaire to all potential anaphylaxis files.

Data analysis

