Based on the data, all three rules will be theoretically applied to all included patients. This will determine which patients would have been dismissed or observed and under what rule. Subsequently, the records of these same patients will be retrospectively analyzed to determine the occurrence of biphasic reaction after the initial visit. It will be particularly interesting to assess whether the biphasic reaction occurred during the emergency observation period.

As we seek to evaluate the effectiveness of diagnostic rules, statistical analyses will focus primarily on a study of sensitivity and specificity. In order to be able to properly characterize the different derived rules, it will also be relevant to obtain the predicted positive and negative values. Confidence intervals will be built around the proportions obtained. The choice of the best derived rule will be based on the sensitivity value obtained. Indeed, we seek to maximize this parameter in order to obtain the combination of variables that will allow us to use a rule to safely discharge patients with low risk of biphasic reaction. In the event that none of the rules maintain a fairly high sensitivity and/or negative predictive value, all Phase 1 and Phase 2 data will be jointly analyzed and a re-derivation test of a statistically stronger rule will be conducted, again using logistic regression models.

Considering that the sample size has been revised, the study schedule has also been revised. It is therefore more realistic for us to expect a period of at least 2 to 3 years to complete the data collection for this phase 2. However, we propose to do an interim analysis of the results at least once a year. Data collection is currently planned for 2020 and 2021 with an initial interim analysis in May 2020. The team is ready to extend the "recruitment" period as needed to reach the 553 patients needed. Data collection is currently well underway and the goal of recruiting 200 to 250 patients per year seems realistic.

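### As written, biphasic reactions are judged from the chart with the predictors already known, and over no stated time window; both can be put right cheaply

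*Combined protocol and SAP*

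**What the plan says.** All references are to the combined protocol and SAP.

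- **Order of work (Methodological, Data analysis).** The section opens with "all three rules will be theoretically applied to all included patients". It then moves on to the outcome: "the records of these same patients will be retrospectively analyzed to determine the occurrence of biphasic reaction after the initial visit". It adds an interest in whether one can "assess whether the biphasic reaction occurred during the emergency observation period".
- **Outcome source (Methodological, Data collection).** "The research team will then review each of these files to assess whether or not there was a biphasic reaction". Clinical significance is judged on the NIAID/FAAN criteria. This text does not place the review before or after the rules are applied. No call or visit to the patient is described for Phase 2.
- **Link to the chart.** The doctor completes the sheet without giving a name, "but will be required to provide the patient's file number".
- **Handling of sheets (Ethical considerations).** The administrative officer takes the sheet out of the chart when the emergency file is closed. Sheets go into sealed envelopes to protect anonymity, and study doctors open them at analysis. A key file ties file numbers to random identifiers, but it is mentioned at the stage when data are counted.
- **Questionnaire (Appendix).** Predictors and an investigators' section with boxes Rb and RBCS are on one form. The abbreviations are not defined; I read them as biphasic reaction and clinically significant biphasic reaction.
- **Use of the result.** "The choice of the best derived rule will be based on the sensitivity value obtained". Sensitivity and/or NPV also decide whether the data are pooled with Phase 1 for a new derivation.
- **Time window.** The Problem section describes risk for up to 72 hours, as background. The methods adopt no window.

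**The concern.** There are two separate issues.

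**Judging the outcome with the predictors known.** Deciding from a chart whether returning symptoms count as a biphasic reaction takes judgement, especially for the all-severities outcome, where no formal criteria are named. A reviewer who has the predictors in hand, or knows how the rule classed the patient, may settle borderline cases differently. The result is then the sensitivity that chooses the best derived rule.

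**Reactions that leave no entry.** Guidelines generally suggest four to six hours of observation, against a risk period of up to 72 hours (Problem section). Actual observation times at the three sites are not given. A reaction after discharge that never reaches the file counts as no reaction. In a rule-negative patient this raises NPV. In a rule-positive patient it lowers PPV and leaves NPV alone.

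**Working it through.** **Step 1. Order of events.** Three places bear on what the outcome reviewer knows.

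1. Data analysis: rules first, chart review next.
2. Appendix: the apparent outcome boxes are on the predictor sheet.
3. Ethical considerations: envelopes are opened at analysis. The key file could lead a reviewer to the chart without the sheet, but it is tied to the counting of data, so it is not clearly available before the envelopes are opened.

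Nothing places outcome coding ahead of opening the sheets. The only order given is the opposite one.

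**Step 2. Number of reactions.** The Sample size section gives sensitivity 98% with "a confidence level of 95% according to an accuracy of 5% and an expected prevalence of 6" per cent, then adds 10%. Buderer's formula is n = z² × Se × (1 − Se) / (d² × prevalence):

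- n = 1.96² × 0.98 × 0.02 / (0.05² × 0.06) = 501.97, so 502
- 502 × 1.10 = 552.2, so 553, which is the plan's figure
- expected reactions of any severity: 502 × 0.06 = 30.1, about 30

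Clinically significant reactions are fewer; their number is not given.

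**Step 3. One borderline case.** Assume 28 of 30 reactions are flagged by a rule: 28/30 = 93.3%.

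| Borderline case judged to be no reaction | Sensitivity | Change |
|---|---|---|
| Rule-negative | 28/29 = 96.6% | up about 3 points |
| Rule-positive | 27/29 = 93.1% | down about 0.2 points |

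The effect comes almost entirely from rule-negative calls, and the two kinds of call pull in opposite directions.

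**Step 4. Unrecorded reactions.** The documents give neither a miss rate nor the number of rule-negative patients, so these are assumptions: 29 of 30 recorded reactions flagged, 250 rule-negative patients and 252 rule-positive.

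- Recorded: sensitivity 29/30 = 96.7%; NPV 1 − 1/250 = 99.6%; PPV 29/252 = 11.5%.
- Equal 25% miss rate in both groups: true sensitivity (29/0.75)/(30/0.75) = 96.7%, unchanged; true NPV 1 − (1/0.75)/250 = 99.5%; true PPV (29/0.75)/252 = 15.3%.
- Three misses, all in rule-positive patients: true sensitivity 32/33 = 97.0%, so the recorded 96.7% is slightly too low; NPV unchanged.

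Thus recorded sensitivity is too high only if reactions are missed more often in rule-negative than in rule-positive patients.

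**The case against.** The case on the other side has real substance.

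- **The sheet shows no rule result.** "The variables were randomly arranged on the questionnaire so that no rules could be recognized or inferred", and the two derived rules need regression weights to score. This stands as mitigation. It is weaker for the literature-based rule, which calls for observation when any one listed item is present and so can largely be read off the sheet.
- **A key file exists.** It does, and it could serve a blinded review. The plan does not say that it is built before the envelopes are opened.
- **Clinical significance has set criteria.** That limits judgement for that outcome. It does not settle whether milder symptoms count as a reaction.
- **No sign of gross under-recording.** The 6% prevalence seen in Phase 1, whose rules were derived retrospectively, is not below the 4 to 5% quoted in the Problem section, although that section also mentions sources as high as 20%. This is reassuring but does not show complete capture.
- **Harm is limited.** No rule is applied to patients in Phase 2, and Phase 3 has systematic follow-up. Both are true, but the rule taken forward is chosen on Phase 2 data.

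A reader might go further and infer that sensitivity is inflated, or that the wrong rule would be chosen. The documents support neither. They give no miss rate, no evidence that misses differ by rule result and no numerical pass mark for sensitivity or NPV. For scale, a recorded 29/30 has an exact 95% interval of 82.8% to 99.9%, so a 3-point shift sits well inside sampling error. That interval does not, however, account for misclassified outcomes.

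**Conclusion.** The point holds as a cheap improvement, not as a demonstrated bias. The plan's stated order, together with outcome boxes on the predictor sheet, leads to outcome coding with the predictors known. One reclassified rule-negative case moves sensitivity by about 3 points and one rule-positive case by about 0.2. The direction is uncertain and no change of ranking is shown.

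Under-recording is the lesser part. Any unrecorded reaction in a rule-negative patient makes recorded NPV too high, but the equal-miss example moves it by only about 0.1 point.

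This rests on my reading of Rb and RBCS, on about 30 reactions from the plan's own inputs, and on assumed counts of flagged reactions, rule-negative patients and misses. The investigators' section is only partly visible in the public text.

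**What to change.** 1. **Reverse the order in Data analysis.** Judge both outcomes from the chart, on a separate form, before envelopes are opened or any rule is applied. Build the key file in advance from a log of file numbers that the administrative officer keeps when removing each sheet. State that blinding is partial, because charts show many of the predictors. Report as a limitation any sheets already opened for an interim analysis.
2. **Fix the window and the search.** Count outcomes over the 72 hours cited in the Problem section, and search the available records of the three sites in the same way for every patient.
3. **Word the result accordingly.** Report recorded biphasic reactions and, where charts allow, observation time by rule result.

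The cost is a log, a second form, some extra chart extraction and a more cautious conclusion. The reviewers, patient care and sample size stay the same. Reactions that were never recorded cannot be recovered by these steps.

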1. PROBLEM

Anaphylaxis is a condition frequently encountered in emergency departments (0.05 to 2% in the general population)¹, which is defined by a severe allergic reaction that appears quickly and has fatal potential. As a result of an anaphylaxis, a serious phenomenon called a "biphasic reaction" can occur. This reaction is the reappearance of anaphylactic symptoms several hours after treatment.

The diagnosis of anaphylaxis is based on the impairment of more than one system (muco-skin, cardiovascular, respiratory, digestive) and its definition, the most recognized, is based on the NIAID/FAAN² criteria developed in 2006 (Box 1). Because of its severity, the treatment of anaphylaxis requires rapid management, which relies mainly on the administration of epinephrine. Other treatments can also be used. Among other things, antihistamics can decrease skin symptoms; intravenous hydration contributes to hemodynamic stabilization; and intravenous corticosteroids may decrease the likelihood of a biphasic reaction. However, the effectiveness of the latter treatment option remains debated in the literature.

The theoretical risk of rebound reaction, or biphasic reaction, is classically described up to 72 hours after the initial anaphylactic event. The biphasic reaction is defined as a recurrence or occurrence of new signs or symptoms after the resolution of the initial reaction, without re-exposure to the allergen³. The potential occurrence of a biphasic reaction often warrants observation of patients for several hours in emergency departments following the management of the initial anaphylaxis. Although the recommendations and guidelines generally propose observation times of four to six hours, there is no clear consensus or evidence to guide this conduct. It may even be suggested to observe patients up to 24 hours^{4,5,6}. To date, there are no prognostic factors to identify a more at-risk patient who would benefit from such an observation. As these reactions are a relatively rare phenomenon (4 to 5%, but could be as high as 20% according to some sources⁵) and the symptoms observed are usually less significant than at the initial presentation⁷, it is therefore possible that a prolonged observation period is not necessary for some patients who do not have high risk factors for biphasic reaction.

Box 1: NIAID/FAAN ANAPHYLAXIS CRITERIA

Presence of one of three following criteria:

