In Phase 1 of the study, two other clinical decision rules were derived retrospectively. By analyzing the characteristics of patients who had an anaphylactic reaction, we were able to derive a rule to identify a low-risk group of biphasic reaction (any symptom of allergy) and clinically significant biphasic reaction (i.e. meeting the criteria for an anaphylactic reaction). These rules were created with the highest possible negative predictive sensitivities and values (VPNs).

The next step is to prospectively verify whether these rules maintain their sensitivity and negative predictive value with a different sample of patients from the same population pool. The first rule assesses the probability of clinically significant biphasic reactions (sensitivity of 90%, 7 variables; Table 3) and the second, all biphasic reactions (100%, 7 variable sensitivity; Table 4). Areas below the ROC curve were 0.896 and 0.874, respectively. Because the variables selected for each decision-making rule come from a regression model, the predicted probability of a biphasic reaction comes from the linear combination of selected variables. Depending on the coefficients calculated, each variable present in the patient will have a different weight in the decision.

TABLE 3: RETROSPECTIVELY DERIVED CLINICAL DECISION RULE FOR CLINICALLY SIGNIFICANT BIPHASIC REACTIONS

| | |
|----|--|
| 1. | ATCD allergy to a different agent than the one in question |
| 2. | Symptoms of diarrhea |
| 3. | ATCD allergy to the same agent as the one in question |
| 4. | Number of doses of O.R. in the emergency room |
| 5. | Food allergen (other than milk, egg, peanuts, seafood) |
| 6. | Number of doses of O.R. before emergency 1 |
| 7. | ENT symptoms |

TABLE 4: RETROSPECTIVELY DERIVED CLINICAL DECISION RULE FOR BIPHASIC REACTIONS (ALL SEVERITIES CONFUSED)

| | |
|----|---|
| 1. | Number of doses of O.R. in the emergency room |
| 2. | Epi doses data different from standard doses (ped: 0.01mg/kg, adult: 0.3-0.5mg) |
| 3. | Symptoms of diarrhea |
| 4. | ATCD allergy to a different agent than the one in question |
| 5. | Secondary anaphylactic reaction to iodine |
| 6. | Secondary anaphylactic reaction to a sting or bite |
| 7. | Secondary anaphylactic reaction to an unknown allergen |

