1. GOALS AND ASSUMPTIONS

The main objective of Phase 2 of our study is to validate prospectively and on a theoretical basis the rules of clinical decisions from previous phases of our research project. This will allow us to assess the internal validity of the different rules derived in the same three circles (Chicoutimi, Jonquière, Alma). In addition, the evaluation of the results will identify the most effective rule.

The hypothesis of this study is that one of the derived rules will, when applied to a cohort of patients prospectively, adequately identify (sensitivity maintained) patients at low risk of biphasic reaction following an anaphylactic reaction.

If the results of the Phase 2 study are successful, a phase 3 will be put forward. The objective of this third phase will be to apply the most effective rule in real time to patients who have undergone an anaphylactic reaction in different hospitals of the RIUSSS of the University of Sherbrooke, i.e. to complete the validation of the rule in a different population.

In the event of an inconclusive Phase 2 result for the three rules under study, the investigators propose to group the data from Phases 1 and 2 to attempt a final diversion of a new clinical decision rule. If this ultimate diversion is quite different from the previously tested rules and is clinically plausible, a new validation attempt will be made (details below).

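### Does choosing the best rule on sensitivity, without naming the outcome, leave the comparison of rules unsound?

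*Combined protocol and SAP*

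**What the plan says.** Two outcomes are in play, one nested in the other. The PROBLEM section gives the broad one: "The biphasic reaction is defined as a recurrence or occurrence of new signs or symptoms after the resolution of the initial reaction". STEPS TAKEN adds a narrower one, limited to recurrences that themselves meet the anaphylaxis criteria. It reports each derived rule on its own target: "The first rule assesses the probability of clinically significant biphasic reactions (sensitivity of 90%, 7 variables; Table 3) and the second, all biphasic reactions", the latter with 100% sensitivity. The next step is to "prospectively verify whether these rules maintain their sensitivity and negative predictive value".

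GOALS AND ASSUMPTIONS says that "the evaluation of the results will identify the most effective rule". In METHODOLOGICAL, Data analysis, all three rules are applied on paper to every included patient. Then: "The choice of the best derived rule will be based on the sensitivity value obtained". The stated purpose is to "use a rule to safely discharge patients with low risk of biphasic reaction". No sentence attaches an outcome to the sensitivity used for selection.

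Both outcomes will be available: under Data collection, the team reviews each file for "whether or not there was a biphasic reaction and whether it was clinically significant". The sample size rests on the unqualified term: "The prevalence of 6% was determined from the prevalence of biphasic reactions observed when collecting Phase 1 data".

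**The concern.** A sensitivity means nothing until the outcome is fixed, and here there are two candidates. A reader who starts from STEPS TAKEN could score the Table 3 rule on clinically significant reactions and the Table 4 rule on all reactions, because a sensitivity can only be maintained against the outcome on which it was measured. If those two figures were then ranked, the comparison would mix the quality of the rules with the definition of the outcome. The Table 3 rule would never be charged for the milder reactions it misses, and with few events a small denominator produces perfect scores more easily. Negative predictive value has the same problem, because it is higher for the rarer outcome whatever the rule.

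The result feeds into which rule is taken to Phase 3 and applied in real time, so a wrong choice would matter.

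**Working it through.** **Event count.** Inputs from Sample size: sensitivity 0.98, half-width 0.05, 95% confidence, prevalence 0.06, 10% allowance for missing data.

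- Events: 1.96² × 0.98 × 0.02 / 0.05² = 30.1
- Evaluable patients: 30.1 / 0.06 = 502
- With the allowance: 502 × 1.10 = 552.2, rounded up to 553, the plan's figure

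The precision was therefore planned on about 30 biphasic reactions, with no restriction on severity.

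**Which outcome the text uses.**

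| Place | Term used |
|---|---|
| PROBLEM, definition | recurrence or any new signs or symptoms |
| GOALS AND ASSUMPTIONS, hypothesis | biphasic reaction, unqualified |
| Sample size, 6% prevalence | biphasic reactions, unqualified |
| Data analysis, outcome determined and purpose of selection | biphasic reaction, unqualified |
| STEPS TAKEN and Data collection, narrower outcome | marked as clinically significant |

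Where the authors mean the narrower outcome, they say so. The literature-based rule (Table 2) is given no severity-specific target and no Phase 1 sensitivity, so ranking each rule on its own outcome could not be carried out for all three rules. The request that sensitivity be maintained concerns validation of each rule, which is a separate use of the figures.

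**What ranking on different outcomes would do.** Assumption: of the 30 events, n = 6, 10 or 21 are clinically significant (20% to 70%); the document gives no share. The Table 3 rule scores X/n and the Table 4 rule Y/30. The entries are the exact binomial probabilities that the Table 3 rule ranks higher v lower; the remainder are ties.

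| True sensitivities (Table 3 rule, Table 4 rule) | How misses relate | n = 6 | n = 10 | n = 21 |
|---|---|---|---|---|
| 95%, 95% | independent | 58 v 26 | 49 v 34 | 47 v 45 |
| 95%, 95% | same patients missed | 52 v 26 | 41 v 32 | 34 v 44 |
| 98%, 98% | independent | 40 v 11 | 37 v 18 | 33 v 31 |
| 98%, 98% | same patients missed | 34 v 11 | 27 v 17 | 17 v 29 |
| 90%, 98% | independent | 24 v 47 | 16 v 64 | 9 v 85 |

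For independent misses, X ~ Bin(n, s₁) and Y ~ Bin(30, s₂). For shared misses, Y = X + Bin(30 − n, s). Shared misses deserve a row because Tables 3 and 4 have three of seven variables in common: emergency-room doses, diarrhoea, and a history of allergy to a different agent. The last row combines the Table 3 rule's Phase 1 figure (90%) with the planning value (98%) for the other rule.

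The sign changes across the table. With equal rules, the smaller event set is favoured at 6 and 10 events, but not at 21 if the misses coincide. With the document's own 90% for the Table 3 rule, the ranking favours the Table 4 rule throughout.

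**On a common outcome.** If both rules are scored on the same 30 events with equal true sensitivity of 95% and independent misses, the split is 38 v 38, so the denominator favours neither rule.

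**The case for a change.** The strongest reply is that leaning towards an outcome is not the same as fixing it. Both outcomes are recorded, no sentence says which one drives selection, and the choice can reverse the winner. Take 30 reactions, 10 of them clinically significant. Rule A catches 10/10 of these and 16/20 of the milder ones; rule B catches 9/10 and 20/20. Scored on different outcomes, A leads with 10/10 = 100% against 29/30 = 96.7%. Scored on all reactions, B leads with 96.7% against 26/30 = 86.7%. Because interim looks are planned at least yearly, an unnamed outcome could in principle be settled after results are seen. Naming it would take one sentence.

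Much of this stands. The outcome is not stated, the Phase 1 figures of 90% and 100% are not like for like, and an explicit sentence would be good drafting. But the reversal needs a ranking that the plan nowhere prescribes, and the consistent wording of the selection text, hypothesis and sample size points to one outcome for all rules. Writing that down would record the best-supported reading and would alter neither the analysis nor the 553 patients.

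POTENTIAL OUTCOMES also brings in ease of application when several rules are effective. How that fits with selection on sensitivity is a separate question, which would remain even if the outcome were named.

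**Conclusion.** No change to the plan is needed. This is a missing detail that an analyst would fill sensibly: score all three rules on all biphasic reactions for selection, and report each derived rule on its own target as validation, without ranking those figures. Both outcomes are already assessed for every patient, so nothing further has to be collected, and the sample size is unaffected.

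The feared bias has no settled direction or size. At 10 of 30 events it runs from 49% v 34% in favour of the Table 3 rule to 16% v 64% against it, depending on the true sensitivities. It also depends on the clinically significant share (assumed here at 20% to 70%) and on how far the rules' misses overlap.

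The conclusion rests on reading the unqualified term as all severities, which the definition and its use throughout support. If the investigators meant to select on clinically significant reactions, the comparison would still be like for like. The precision would be weaker: with 10 such events the half-width is 1.96 × √(0.98 × 0.02 / 10) = 8.7 points, against the planned 5.

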1. POTENTIAL OUTCOMES

If one of the clinical decision rules is sufficiently effective during this phase of the study (phase 2), i.e. maintaining good sensitivity and negative predictive value, it can be applied in real time. If more than one rule is effective, the most easily applicable rule will be chosen. This will be done as part of a phase 3 study with systematic follow-up for each patient for whom the rule has been applied.

If Phase 3 proves it is conclusive, the rule demonstrates a strong negative predictive value during its actual clinical use and good external validity, and it will be disseminated on a larger scale. Thus, we hope to facilitate the management of anaphylaxis in the emergency room by allowing **the early and safe release** of many patients who have been treated for an anaphylactic reaction, ensuring that the risks of biphasic reactions are minimized.

The rule bearing the name of the geographic region from which it originates could help to spread the environment of the CIUSSS SLSJ. In addition, having received financial assistance and support from the MF/MU department of the University of Sherbrooke, the investigators will ensure that the name of the University and the Department they represent is clearly visible in their publication; also helping to spread the way of this institution.

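### Choosing the best of three rules by observed sensitivity, and estimating its sensitivity on the same 30 or so events without correction, overstates that sensitivity on average by about 0.5 to 4.4 points

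*Combined protocol and SAP*

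**What the plan says.** The Goals and Assumptions section expects that "the evaluation of the results will identify the most effective rule". The Methodological section starts from two derived rules and one literature-based rule, and under Data analysis "all three rules will be theoretically applied to all included patients". On inference it says only "Confidence intervals will be built around the proportions obtained", without naming an interval type. On selection it says "The choice of the best derived rule will be based on the sensitivity value obtained", and explains that sensitivity is the parameter to be maximised. The word derived leaves some doubt whether the literature-based rule competes for selection.

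The Potential Outcomes section has a different rule: "If more than one rule is effective, the most easily applicable rule will be chosen". It gives no numerical threshold for effective.

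Neither section describes an optimism correction, a simultaneous interval, a split sample, a pre-named primary rule or a paired comparison between rules. Phase 3, in a different population, follows only if Phase 2 succeeds.

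**The concern.** The largest of several noisy estimates is, on average, larger than the true value of the rule that produced it. Here the same events choose the rule and measure it. With about 30 events one patient moves sensitivity by 1/30 = 3.3 points, so a single patient can decide which rule is called best.

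The error runs in the unsafe direction: the chosen rule appears to miss fewer biphasic reactions than it does. Phase 2 also decides whether a rule goes forward to real-time use in Phase 3 or whether a new rule is derived. The schedule allows publication of the Phase 2 results before Phase 3.

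**Working it through.** **The plan's own figure.** The Sample size subsection gives sensitivity 98%, confidence 95%, precision 5%, prevalence 6% and a 10% allowance for missing data. Buderer's formula, with z = 1.96 (two-sided, inferred because it reproduces the total):

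n = 1.96² × 0.98 × 0.02 / (0.05² × 0.06) = 502 after rounding up; 502 × 1.10 = 552.2, rounded up to 553.

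This matches the plan. Expected events are 0.06 × 502 = 30 with the allowance fully used, or 0.06 × 553 = 33 with no losses.

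**One rule against the best of three.** Assume each rule is truly 90% sensitive (the Phase 1 value of one derived rule) and there are 30 events.

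- One pre-named rule: P(at least 29/30) = 30 × 0.9²⁹ × 0.1 + 0.9³⁰ = 0.141 + 0.042 = 0.18.
- Best of three independent rules: 1 − (1 − 0.184)³ = 0.46.
- With latent correlation 0.5 and 0.8, by simulation: 0.41 and 0.36.

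**Mean overstatement of the selected rule.** Simulation of three correlated rules on the same 30 events, with ties broken at random. True sensitivities and correlation are assumptions.

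| True sensitivities | Correlation 0 | 0.5 | 0.8 |
|---|---|---|---|
| 90/90/90 | +4.4 | +3.8 | +3.0 |
| 95/95/95 | +3.1 | +2.7 | +2.1 |
| 98/98/98 | +1.7 | +1.5 | +1.2 |

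With one clearly best rule (98/90/85) the range is about +0.5 to +1.2. With 33 events the three equal-rule rows become +4.2 to +2.9, +2.9 to +2.1 and +1.6 to +1.2. If only two rules compete, both at 90%, the range is +2.0 to +3.0. When the three rules are equal, the top two differ by at most one event in 66 to 98% of runs.

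**Intervals after selection.**

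- Clopper-Pearson and Wilson 95% intervals still cover the truth in at least 97% of runs at true sensitivities of 90 to 98%.
- Their lower limits move up. With three rules at 95%, the mean Clopper-Pearson lower limit is 80.7% for one pre-named rule and 83.8 to 85.3% for the selected one.
- The Wald interval, the form behind the sample-size formula, has zero width at 30/30. With equal rules its lower limit lies above the truth in 36 to 91% of runs after selection, and in 18 to 55% for a single rule.

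**Simultaneous lower limit.** For three rules, 1 − 0.05/3 = 98.3%. At n/n the exact lower limit is (α/2)^(1/n). At 30/30 this is 0.025^(1/30) = 88.4% for a 95% interval and (0.05/6)^(1/30) = 85.2% for 98.3%. At 29/30 the limits are 82.8% and 79.3%.

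**The alternative selection rule.** Choosing the easiest rule among those that pass also conditions on the same data. Take an assumed pass mark of 95%, that is at least 29/30. At true 90% the mean among passing results is (0.141 × 29/30 + 0.042)/0.184 = 97.4%, an overstatement of about 7.4 points. At true 98% it is about 0.7 points.

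**The case against.** **Ties are near the worst case.** The bias is largest when the rules are equally good. Phase 1 gave 90% and 100% for the two derived rules, and the plan assumes at least 98%. At 98% the average bias cannot exceed 2 points, because no estimate exceeds 100%. This stands, and it is why a range is needed.

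**Correlation helps.** The derived rules share epinephrine doses in the emergency department, diarrhea and allergy to a different agent. At correlation 0.8 the bias at 90/90/90 falls from 4.4 to 3.0 points, about a third. The bias shrinks but does not disappear.

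**The intervals.** A reader might infer that the planned intervals become invalid. The documents do not support that: no type is named, and exact or Wilson intervals keep their coverage at this event count. Only the upward shift of the lower limit, and the poor behaviour of Wald limits, can be claimed.

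**Safety.** A reader might infer that an inflated figure would put an unsafe rule into general use. The text does not go that far. No rule is applied to patients in Phase 2, negative predictive value is also considered, and Phase 3 re-estimates the rule with systematic follow-up before wider dissemination. That reduces the consequence, but Phase 3 starts only for a rule already selected on these data.

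**The bootstrap is a partial remedy.** It removes only about 40 to 60% of the bias when the rules are equal, and takes only about 0.5 point from a 30/30 winner. With all rules at 98%, the winner is 30/30 in 79 to 91% of runs. It should be offered as a reduction of the bias.

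**Conclusion.** The point holds. As written, the plan overstates the selected rule's sensitivity on average, and it lets a difference of one event patient rank the rules. With 30 events and latent correlation 0 to 0.8, the overstatement runs from about 0.5 points (one rule clearly best) to 4.4 points (three independent rules at 90%), against a planned precision of 5 points. Where in that range the study falls cannot be known from the documents, and a reader should not take the upper end as the expected size.

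Two features of the plan add to it. The selection rules under Data analysis and Potential Outcomes conflict, and both use the same data. The derived rules also target different outcomes (clinically significant and all biphasic reactions), and no common outcome is stated for the comparison. Clinically significant reactions would be no more frequent than all reactions, and fewer events enlarge the bias: with an assumed 15 events the range is 1.3 to 6.0 points.

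**What to change.** 1. Reconcile the Data analysis and Potential Outcomes sections into one selection rule, applied to one common outcome, and say whether all three rules compete.
2. Report all three rules side by side with exact or Wilson intervals, not Wald, and with paired differences in sensitivity. Do not call one rule better when the paired interval includes zero.
3. Beside the selected rule's raw sensitivity, report a bootstrap optimism-corrected value: resample patients, score all the rules, repeat the selection, and subtract the mean optimism. State that this removes only part of the bias and does little when the winner is 30/30.
4. Base the Phase 3 decision on the lower limit of a simultaneous interval, for example 98.3% exact, and not on the point estimate of the maximum.

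No new patients or data are needed. The cost is a change of analysis wording, a few hours of programming and a less favourable lower limit (85.2% instead of 88.4% at 30/30). The corrected point estimate would be lower than the raw one by about 0.5 to 2.7 points on average in the scenarios above.
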